28.0 Study Plan - Details

28.1 Research Methods - Include the Schedule of Events or provide a precise description of the data collection methods. (Attach the Schedule of Events to the Initial Review Submission Form, if applicable)

Overview of Study Design.

A total of 50 subjects per study will be randomly assigned to double-blind, subchronic dosing with active drug (n = 25) or matched placebo (n = 25). Subjects will meet the Diagnostic and Statistical Manual – 5th Edition (DSM V) criteria for alcohol use disorder of at least moderate severity (AUD-MS) and be non-treatment-seeking, to avoid exposing treatment-seeking individuals with AUD-MS to alcohol cues. Alcohol abstinence is required during the last 3 days of the dosing period in order to test the effect of study drug when motivational symptoms of early abstinence are manifest. Human lab testing occurs on the last day of dosing/third day of abstinence.

Subjects are presented with 12 positive, negative or neutral affective images selected from the International Affective Picture System on a flatscreen monitor (IAPS). Each affective condition is followed by in vivo exposure to the subject's preferred alcoholic beverage or bottled water, which the subject is told to view and smell for 90 seconds and to not drink it. Endpoints selected assess the effects of drug relative to placebo on responsivity to in vivo alcohol cue exposure in the lab, as well as on naturalistic measures of drinking, affect, and craving through 1-month posttreatment.

These methods inform the 3 stages of the addiction cycle: preoccupation/anticipation (craving), binge/intoxication (drinking quantity and frequency, binge drinking) and negative affect (mood, anxiety). Craving in response to alcohol cue exposure in the lab has been reliably predictive of subsequent drinking in alcoholics, and thus craving in response to in vivo alcohol cue exposure in the laboratory comprises the primary outcome for this proof-of-concept study. Self-reported drinking data are collected as a secondary outcome variable, as the 3-day abstinent interval constrains complete evaluation of this variable, and drinking data are collected under less

controlled conditions than craving in response to in vivo alcohol cue exposure in the lab.

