41.8 Proposed Funding Date - END								
01/31/2022								
41.9 Are part of or all activities in this proposal funded by a training grant?								
O Yes 6 No								

NCT03175549

Medication Development in Alcoholism: Apremilast versus Placebo

IRB Summary of Amendments-06/01/2017-05/08/2020

Summary of Amendments for NCT03175549

2017 Continuing Review Application-Prior to Study Initiation

Submitted on 06/01/2017/Approved on 06/19/2017

In the current application, we propose amending the final fixed dose of apremilast from 60 mg (30 mg/bid) for 5 days to a final fixed dose of 100 mg (50 mg/bid) for 5 days based on the pre-clinical data.

Animal data showed apremilast in dose of 10 mg/kg (human equivalent of 56 mg per day) was ineffective for reducing alcohol consumption and achieved efficacy in dose of 20 mg/kg which equivalents to human dose of 112 mg per day. This information was communicated to [name] in a personal email correspondence dated 05/26/17 from [name], an INIA collaborator at the University of Texas-Austin.

We searched the Clinical Pharmacology and Biopharmaceutical Review for apremilast and noted doses up to 100 mg per day have been studied. A series of studies showed any side effects (primarily diarrhea) are successfully reduced through dose titration and dosing on a twice a day schedule. Therefore, we are requesting IRB approval to treat 25 subjects on 5 days of a final fixed dose of 100 mg (50 mg BID) per day after a 7-day titration starting at 10 mg per day and increasing in 10 mg doses and 25 subjects on placebo. The titration to 100 mg per day will be according to the following schedule:

Day 1: 10 mg in morning

Day 2: 10 mg in morning and 10 mg in evening

Day 3: 10 mg in morning and 20 mg in evening

Day 4: 20 mg in morning and 20 mg in evening

Day 5: 20 mg in morning and 30 mg in evening

Day 6: 30 mg in morning and 30 mg in evening

Day 7: 30 mg in morning and 40 mg in evening

Day 8: 40 mg in morning and 40 mg in evening

Day 9: 40 mg in morning and 50 mg in evening

Day 10: 50 mg in morning and 50 mg in evening

Day 11: 50 mg in morning and 50 mg in evening

Day 12: 50 mg in morning and 50 mg in evening

Day 13: 50 mg in morning and 50 mg in evening

Day 14: 50 mg in morning and 50 mg in evening

Based on this titration schedule, we request modifying the duration of study drug administration from 10 days to 14 days.

Amendment-Prior to Study Initiation

Submitted on 07/20201/Approved on 08/11/2017

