- -Added [name] as the Sub Investigator and Study Contact Person.
- -Changed the visit schedule.
- -Removed the Structured Clinical Interview for the DSM-IV (SCID) and replaced it with the Mini International Neuropsychiatric Interview (MINI) for DSM-V criteria.
- -Added the Columbia Suicide Severity Rating Scale (CSSRS) to the screening visit.
- -Removed the Profile of Mood States (POMS) from the self-report battery.
- -Added that subjects will be stratified by sex and by High-sensitivity C-reactive Protein (hs-CRP).
- -Added obtaining blood to visits two and four.
- -Added Cytokine analysis that will be performed at the end of the study by [name] at Temple University's School of Medicine.
- -Added medication over-encapsulation by Austin Compounding Pharmacy in Austin, TX.
- -Eliminated the need for women of child bearing age to use an effective form of birth control for 2 weeks following study duration. Revised to through study duration.
- -Removed "History of Seizure Disorder" from exclusion criteria.
- -Changed recruitment website from www.pearsoncenter.org to www.tsriaddiction.com.

- -Clinicaltrials.gov number obtained NCT03175549
- -Added a urine drug screen (UDS) at visit two.
- -Added the Columbia Suicide Severity Rating Scale (CSSRS) at visit four

Amendment-Prior to Study Initiation

Submitted on 09/28/2017/Approved on 10/13/2017

-Changed the dose range from 10 mg to 100mg/day to 10 mg to 90 mg/day and revised the dosing schedule.

Amendment

Submitted on 05/17/2018/Approved on 06/08/2018

Revised upper age limit to include subjects above the age of 65.

Revised the exclusionary criteria regarding positive urine drug screens to allow subjects who test positive for THC to participate in the study as long as they do not meet DSM-V criteria for cannabis use disorder at a moderate level or greater, and that these subjects agree to maintain three days of abstinence from cannabis prior to the laboratory session at the fourth visit of the study.

Amendment

Submitted on 08/30/2018/Approved on 10/12/2018

Obtained permission to collect serum at Visit 2 and Visit 4 to assay endotoxins to rule out a factor other than alcohol as a source of abnormal cytokine activity.

Amendment

Submitted on 05/15/2019/Approved on 07/12/2019

Expanded the inclusion criteria to enroll subjects who do not meet current criteria for depression who have been on a stable dose of anti-depressant medication for at least 3 months.

Amendment

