NCT03175549

Medication Development in Alcoholism: Apremilast versus Placebo

Statistical Analysis Plan Date: 01/20/2017

Statistical Analysis Plan, Demographic and baseline clinical characteristics will be examined for group differences by Fisher's Exact test for categorical/dichotomous variables and ANOVA for continuous variables. Variables will be tested individually for correlation to each outcome variable by Pearson's product-moment correlation or χ^2 , as appropriate. Any variable significantly associated with outcome or differing between treatment groups will be evaluated in all subsequent analyses as a covariate and will be retained if it reduces the residual variance, or otherwise will be left out of the model. Potential covariates of interest include baseline value of a measure, baseline values of peripheral markers of inflammation and stress response, sex. family history of alcoholism, smoking, and age of onset of heavy drinking. 98,99,100 Hypothesis: Subjects treated with active drug (apremilast) will report significantly lower VAS craving ratings in response to in vivo alcohol cues during human lab testing than placebo treated subjects. Repeated measures mixed effects models (MEM)¹⁰¹ will be used to examine drugplacebo differences in VAS craving ratings in response to beverage exposure (alcohol vs. water), where drug is treated as a fixed, between-subjects variable and beverage presentation is the repeat measure. Beverage will be considered a fixed, within-subjects variable and subject as a random effect. Drug effects on naturalistic secondary outcomes, i.e., drinking, will be examined using repeat MEM, as above Safety evaluations: Rates of treatment-emergent signs and symptoms will be computed for each treatment group by body system (e.g., liver, hematologic). Changes and trends in laboratory results will be examined based on shift tables and scatter plots. Relationship to exposure (dose and time) to study drug will be examined. χ^2 analyses will be used to compare the drug groups on rate of study discontinuation due to adverse reactions and overall.

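### Sex and hs-CRP became stratification factors after the only SAP supplied was written, so a screen on outcome data, not the design, decides whether they are modelled: a small gap, nearly free to close

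*Protocol*

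**What the plan says.** Protocol section 28.1 (Overview of Study Design) describes simple two-arm allocation, with no strata: subjects are "randomly assigned to double-blind, subchronic dosing with active drug (n = 25) or matched placebo (n = 25". The Summary of Amendments at the end of the Protocol later lists, in an entry marked as preceding study initiation and "Approved on 08/11/2017", the line "Added that subjects will be stratified by sex and by High-sensitivity C-reactive Protein (hs-CRP". It gives no hs-CRP cut-point, and it does not say whether stratified allocation, stratified analysis or both are meant.

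The SAP is headed "Statistical Analysis Plan Date: 01/20/2017". Its covariate rule has three parts:

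- Screening: "Variables will be tested individually for correlation to each outcome variable".
- Entry: "Any variable significantly associated with outcome or differing between treatment groups will be evaluated in all subsequent analyses as a covariate".
- Retention: a covariate "will be retained if it reduces the residual variance, or otherwise will be left out of the model".

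The candidates are listed as follows: "Potential covariates of interest include baseline value of a measure, baseline values of peripheral markers of inflammation and stress response, sex". Sex is therefore named. hs-CRP is covered only generically, as an inflammation marker, and as a baseline value rather than a stratum.

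The SAP words the primary hypothesis as lower craving ratings to alcohol cues on drug than on placebo. The model it then describes has drug between subjects, beverage (alcohol or water) within subjects and subject as a random effect. It does not say which contrast of that model is the primary test.

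**The concern.** When allocation is stratified, the usual practice is for the primary model to carry the stratification factors because of the design. Here they must earn their place. The imbalance route is nearly closed, because stratified allocation is meant to prevent imbalance on exactly these factors. That leaves the outcome route: a significance test of each factor against the trial's own outcome, at a level the SAP does not state. The content of the primary model is therefore unknown until the outcome data are in.

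Two features of the SAP make the model less certain still. Variables are tested against each outcome separately, yet one that passes is evaluated in all later analyses. And because the primary contrast is not named, it is unclear whether adjustment would reach it at all. At stake are pre-specification and some precision.

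**Working it through.** **Inputs.** From the documents: 50 subjects, 25 per arm (section 28.1); six ratings per subject, 3 affects by 2 beverages (section 28.1, Visit 3); SAP dated 01/20/2017; amendment approved 08/11/2017, just under seven months later. The documents give no alpha, power, effect size, SD, hs-CRP cut-point or within-subject correlation. Section 37.8 justifies the number of subjects only by the yield from consent to enrolment, so 50 cannot be reproduced. For orientation, at an assumed two-sided 0.05 and 80% power the detectable difference is (1.960 + 0.842) × sqrt(2/25) = 0.79 SD. Effects of 0.80 or 0.81 SD are used below.

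**1. How demanding is the screen?** At an assumed 0.05 and n = 50, a factor passes if |r| > 2.011 / sqrt(2.011² + 48) = 0.279. By Fisher's z, the chance of passing is 1 − Φ(1.96 − atanh(r) × sqrt(47)), plus a negligible lower tail:

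- true r = 0.2: 29%
- true r = 0.3: 56%

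For a moderately prognostic factor, inclusion is close to a coin toss.

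**2. Alcohol-cue contrast: screened against mandatory.** Simulated trials assumed 25 per arm, a 0.81 SD effect, a median split for hs-CRP, and sex and hs-CRP each carrying half the explained variance. The screen was applied to the continuous hs-CRP value, as the SAP's wording suggests. If craving is linear in hs-CRP (6,000 trials per row):

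| Variance explained | Power, SAP screen | Power, mandatory stratum | Change (points) |
|---|---|---|---|
| 5% | 80.8% | 81.8% | +1.0 |
| 10% | 82.1% | 83.3% | +1.2 |
| 20% | 86.8% | 87.4% | +0.6 |
| 30% | 90.4% | 89.8% | -0.6 |

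The simulation error of each power is about sqrt(0.85 × 0.15 / 6000) = 0.5 points. A second simulation of the linear case gave changes between +0.4 and -1.5. If craving instead steps at the cut-point, the two simulations gave gains of 1.5 to 3.8 and about 0.5 to 3 points. The overall range is therefore about -1.5 to +4.

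If the screen is applied to the binary stratum itself (mixed model, one rating per beverage, within-subject correlation 0.5), power is 82.0/83.4/87.2/91.5% with the screen and 82.5/84.4/88.1/92.1% with mandatory terms, at 5/10/20/30% explained.

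**3. Drug by beverage.** Let D be a subject's alcohol rating minus water rating. Under a random intercept, the subject effect and every covariate main effect appear in both ratings and cancel from D. With complete ratings the drug-by-beverage estimate is the difference between arms in mean D, so main effects cannot move it. REML fits to simulated data with six ratings per subject agree:

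- Complete data: -1.439246 (SE 0.44123) both with and without sex and hs-CRP main effects.
- 10% of ratings missing: -1.019 (SE 0.5005) without and -1.030 (SE 0.5003) with them.
- The drug effect at the alcohol cue does respond (complete data): -0.646 (SE 0.589) without and -0.598 (SE 0.567) with them.

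Only factor-by-beverage terms reach this contrast, and they matter only if the factors change D. Suppose the factors act at the alcohol cue alone (one rating per beverage, correlation 0.5, strata explaining 5/10/20/30% of variance there):

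| | Without factor-by-beverage terms | With them |
|---|---|---|
| Power | 80.7/81.9/82.8/83.3% | 81.9/84.6/88.2/91.6% |
| Type I error | 4.3/3.9/3.1/2.2% | 4.9 to 5.2% |

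**4. The two readings of the screen.** Testing outcome by outcome, or letting a factor that passes for one outcome count for both, gives 83.8% against 84.0% power at 10% explained and 87.4% against 87.8% at 20%. The gap never exceeds 0.4 points. Type I error is 4.6 to 5.2% under both readings and with mandatory terms.

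**The case against.** The case for leaving this alone has real force.

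- **Evidence.** Stratification appears in one line of an amendment summary. The amended protocol, the randomisation procedure and any later SAP are not supplied. That stratified allocation is meant is an inference, and a later SAP cannot be excluded. This stands, and the point is conditional on it. The line does, however, post-date the SAP, so it does not describe superseded text.
- **Already partly handled.** The SAP names sex and inflammation markers and gives entry and retention rules. The fair comparison is therefore screened against mandatory, not unadjusted against adjusted. This stands too. The unadjusted comparison would show about 1.5 to 8 points, which overstates the cost of this SAP.
- **Dichotomising.** A forced stratum can do slightly worse than the SAP's continuous hs-CRP value when the relation is linear, as the last row of the first table shows. This stands, and is why the role of continuous hs-CRP should be settled in advance.
- **Interaction terms.** The SAP does not say that covariates enter only as main effects. That is the ordinary reading, and the cancellation in step 3 depends on it.
- **Separate issues.** The unnamed contrast and the two readings of the screen would exist without the amendment. They belong here only because they decide whether adjustment has any effect.

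None of this removes the core: the design uses these factors, and the only plan supplied leaves their place in the model to outcome data.

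**Conclusion.** The point holds as a low-priority improvement to pre-specification. Relative to the SAP's screen, mandatory terms change power for the alcohol-cue contrast by roughly -1.5 to +4 points. This assumes an effect of about 0.8 SD, two-sided 0.05, a two-level hs-CRP factor split at the median, and strata explaining 5 to 30% of variance. The sign depends on whether craving is linear in hs-CRP or steps at the cut-point, which nobody can know from these documents. For drug by beverage, main effects change essentially nothing. Leaving out factor-by-beverage terms costs power only if the factors alter the alcohol-minus-water difference, and the test is then conservative.

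A reader might infer more than this:

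- **Inflated type I error from ignoring the strata.** Not supported. The simulated error rate stays near 5% with the screen and falls below it when prognostic strata are left out.
- **Invalid or seriously underpowered primary analysis.** Not supported. The larger losses need drug by beverage as the primary test, factors acting only at the alcohol cue, and 20 to 30% of variance explained. The documents establish none of these.
- **Adjustment can never affect drug by beverage.** Too strong. It is exact only with complete ratings, a random intercept and covariates as main effects.

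**What to change.** Before unblinding, amend the SAP to:

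1. Make sex and the hs-CRP stratum, as used at allocation, fixed effects in the primary craving model and the secondary drinking models, exempt from the screen.
2. State in advance whether baseline hs-CRP is also entered as a continuous value.
3. Include sex by beverage and hs-CRP by beverage in the craving model, so that the adjustment reaches either contrast.
4. Name the primary contrast: the drug difference at the alcohol cue, as the hypothesis is worded, or drug by beverage.

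Confirm from the amended protocol that the stratification refers to allocation, and record the cut-point. If it does not refer to allocation, the point reduces to fixing these covariates in advance. Protocol section 37.13 has the blind broken after the last subject's follow-up; the documents do not say whether that has happened.

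The cost is SAP wording and a few degrees of freedom (four terms if hs-CRP has two levels). At subject level the critical t moves from 2.011 (48 df) to 2.013 (46 df). If neither factor is prognostic, simulated power falls from 81.0% to 80.7% at the alcohol cue and from 80.1% to 79.9% for drug by beverage, which is under about 0.5 points either way.

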NCT03175549

Medication Development in Alcoholism: Apremilast versus Placebo

Statistical Analysis Plan Date: 01/20/2017

Statistical Analysis Plan, Demographic and baseline clinical characteristics will be examined for group differences by Fisher's Exact test for categorical/dichotomous variables and ANOVA for continuous variables. Variables will be tested individually for correlation to each outcome variable by Pearson's product-moment correlation or χ^2 , as appropriate. Any variable significantly associated with outcome or differing between treatment groups will be evaluated in all subsequent analyses as a covariate and will be retained if it reduces the residual variance, or otherwise will be left out of the model. Potential covariates of interest include baseline value of a measure, baseline values of peripheral markers of inflammation and stress response, sex. family history of alcoholism, smoking, and age of onset of heavy drinking. 98,99,100 Hypothesis: Subjects treated with active drug (apremilast) will report significantly lower VAS craving ratings in response to in vivo alcohol cues during human lab testing than placebo treated subjects. Repeated measures mixed effects models (MEM)¹⁰¹ will be used to examine drugplacebo differences in VAS craving ratings in response to beverage exposure (alcohol vs. water), where drug is treated as a fixed, between-subjects variable and beverage presentation is the repeat measure. Beverage will be considered a fixed, within-subjects variable and subject as a random effect. Drug effects on naturalistic secondary outcomes, i.e., drinking, will be examined using repeat MEM, as above Safety evaluations: Rates of treatment-emergent signs and symptoms will be computed for each treatment group by body system (e.g., liver, hematologic). Changes and trends in laboratory results will be examined based on shift tables and scatter plots. Relationship to exposure (dose and time) to study drug will be examined. χ^2 analyses will be used to compare the drug groups on rate of study discontinuation due to adverse reactions and overall.

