Subjects return 1 week and 1-month after drug discontinuation to assess any persisting effects on naturalistic measures of drinking, craving and affect. A positive signal on such indices would lend support to the potential utility of the drug in the treatment of AUD-MS and identify endpoints likely to show a positive drug effect in clinical trials.

Study Procedures:

Visit 1-Screening: After providing written informed consent, subjects complete the Screening Visit for initial evaluation of eligibility. A mini-cue session familiarizes subjects with the human lab setting and identifies non- cue-reactive subjects for study exclusion (Visual Analogue Scale [VAS] craving rating of alcohol cue < 3 points higher than water cue).

Visit 2-Randomization: Subjects complete the evaluation for eligibility. Medically cleared subjects complete baseline assessments and are randomized to receive a blistercard containing the double-blind study drug. A phone call is scheduled for Day 3 (and Day 7 in studies having 8-10 days of drug exposure) to address any questions or concerns and assess compliance.

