37.0 Study Population	
*Briefly describe your targeted population. (Patients with a condition or disease, healthy control subjects, etc.)	
We are looking to recruit 50 paid, non-treatment-seeking, alcohol-dependent but otherwise healthy male and female volunteers between the ages of 18 and 65.	
37.2 *Explain rationale for using human subjects.	
The purpose of this study is to evaluate the efficacy of apremilast as a potential treatment for alcohol use disorder of moderate or greater severity; therefore, use of humans is essential to determining the efficacy of apremilast as a potential treatment in this disorder.	
37.3 *Age	
Age Range Not Applicable	
Enter the specific age range for study population.	
From:	
18	
To:	
65	
37.4 *Gender	

decreased craving for alcohol following alcohol cue exposure in the laboratory and report fewer symptoms of protracted abstinence (e.g., craving, relapse to drinking, mood and sleep

disturbances) under naturalistic conditions, relative to those treated with placebo. This will allow

O Male
⊕ Both male and female
37.5 *How many subjects are you planning to enroll at this institution/site?
50
If this is a chart review, indicate the number of charts: (If this is not a chart review, enter θ .)
0
If necessary, provide explanation below.
37.6 *How many subjects will be enrolled at ALL sites? (Include Scripps and NON-Scripps)
50
If necessary, provide explanation below.
37.7 To achieve your needed number of subjects, how many subjects do you estimate will need to give informed consent? (Allowing for screen failures)
100
37.8 *Justification for the number of subjects required:
Previous studies in our lab have shown that we need to give informed consent to 100 subjects in order to enroll the 50 subjects required for the study.
37.9 Please check all potentially vulnerable populations that are included:
* Regulated
Children / Minors (subjects less than 18 years) *
Pregnant Women *
Prisoners *
☐ Economically or educationally disadvantaged persons
Non-ENGLISH speaking
Diminished mental capacity
Physically disabled
☐ Students
Scripps Health Employees
Scripps Research Institute Employees
Other
If other, describe.

If including vulnerable subjects, explain why. Explain what safeguards are included to protect against coercion or undue influence.

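### The covariate rule turns on an undefined 'residual variance'; read as the within-subject residual of the planned mixed model, it cannot see subject-level covariates, including both stratification factors

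*SAP*

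**What the plan says.** The SAP is one paragraph dated 01/20/2017. It tests each baseline variable against each outcome and between arms, then states: "Any variable significantly associated with outcome or differing between treatment groups will be evaluated in all subsequent analyses as a covariate". A variable so evaluated "will be retained if it reduces the residual variance, or otherwise will be left out of the model". The candidates are described thus: "Potential covariates of interest include baseline value of a measure, baseline values of peripheral markers of inflammation and stress response". The list continues with sex, family history, smoking and age of onset of heavy drinking.

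The primary model is a repeated-measures mixed model with drug as the between-subject factor: "Beverage will be considered a fixed, within-subjects variable and subject as a random effect". The hypothesis is that subjects on active drug "will report significantly lower VAS craving ratings in response to in vivo alcohol cues during human lab testing than placebo treated subjects".

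Two facts in the protocol bear on this. The Summary of Amendments (approved 08/11/2017, after the SAP date) adds stratification by sex and hs-CRP. Section 28.1 (Visit 1) describes a mini-cue session that rates craving to alcohol and to water before randomisation and excludes subjects with "Visual Analogue Scale [VAS] craving rating of alcohol cue < 3 points higher than water cue".

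**The concern.** A model with a random subject effect splits unexplained variation into a between-subject part and a within-subject part. Mixed-model output usually labels the second one 'residual', so reading the rule that way is natural. The SAP does not name the component, the estimator, or how large a reduction counts.

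This matters because most of the listed candidates take one value per subject. Entered as main effects, they explain differences between subjects, not differences among one subject's ratings. A rule that looks only at the within-subject residual is therefore blind to what they contribute. Yet the hypothesis as worded compares arms at the alcohol cue, where between-subject variance dominates the standard error.

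The strata raise a second issue. No sentence in the SAP keeps sex and hs-CRP in the model. Leaving out prognostic factors used to balance the randomisation makes the test conservative.

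**Working it through.** **Inputs from the documents.** 25 per arm and six ratings per subject (three affect conditions by two beverages), from Section 28.1. Random subject effect, drug and beverage fixed, from the SAP. 100 consents for 50 enrolled, from Sections 37.7 and 37.8.

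**Inputs assumed, because the documents give none.** Total variance 1 with ICC 0.5 (between 0.5, within 0.5); effect 0.81 SD of the alcohol-cue mean, which gives about 80% power unadjusted; two-sided alpha 0.05 for screen and test; correlation r of a subject-level baseline with the alcohol-cue mean of 0.3, 0.5 or 0.7. The plan has no figure of its own to reproduce.

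**Step 1: the residual does not move.** In complete balanced data with a between-subject variance estimate above zero, the REML residual is the within-subject sum of squares over N − n − 2 = 300 − 50 − 2 = 248 (the 2 being beverage and drug-by-beverage). A covariate x constant within subject has no deviation from its subject mean, so it changes neither numerator nor denominator.

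Simulation agrees (60 datasets per setting, between and within variance 1 each, covariate explaining 40% of the between-subject variance):

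| Ratings per subject | Within-subject residual | Between-subject variance | SE of drug effect | SE of drug-by-beverage |
|---|---|---|---|---|
| 2 | 1.0295 → 1.0295 | 1.011 → 0.572 | 0.347 → 0.296 | 0.405 → 0.405 |
| 6 | 0.9802 → 0.9802 | 0.995 → 0.594 | 0.303 → 0.248 | 0.228 → 0.228 |

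The residual fell in 0% of datasets, under REML and ML, while the drug SE fell by about 15% and 18%.

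**Step 2: what this costs at the alcohol cue.** The variance of a subject's mean over three alcohol ratings is 0.5 + 0.5/3 = 0.667, so the SE of the arm difference is √(2 × 0.667/25) = 0.231. Adjustment multiplies it by √(1 − r²), giving 0.220 / 0.200 / 0.165. The noncentrality is 0.81/√(2/25) = 2.864 unadjusted (48 df) and 2.864/√(1 − r²) = 3.00 / 3.31 / 4.01 adjusted (47 df). Power is 80% unadjusted and 84 / 90 / 98% adjusted.

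Simulating the whole procedure (1,200 runs per cell, complete data):

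| | r = 0.3 | r = 0.5 | r = 0.7 |
|---|---|---|---|
| Passes the significance screen | 53% | 94% | 99.9% |
| Kept, within-subject reading | 0% | 0% | 0% |
| Power, within-subject reading | 79–80% | 79–80% | 79–80% |
| Power, total-variance reading | 82% | 89% | 98% |
| Power, fixed adjustment | 83% | 90% | 98% |

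The drug-by-beverage SE is √(2 × (2 × 0.5/3)/25) = 0.163 with or without the covariate. At smaller effects the gain has the same form: at 0.5 SD, power rises from about 41% to 44 / 51 / 67%.

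**Step 3: a few missing ratings.** With 5% of ratings missing, the median relative change in the residual was 0.005% for pure noise and 0.08% at r = 0.7. Among covariates that passed the screen, the rule kept 49% of noise variables and 55 / 51 / 54% of prognostic ones, so retention is near chance. Power was 79 / 85 / 89%, against 80 / 90 / 97% with fixed adjustment.

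**Step 4: range restriction from the cue gate.** Since "we need to give informed consent to 100 subjects in order to enroll the 50 subjects required for the study", at most half of those consented can fail the gate. Truncating a normal baseline at its median leaves u² = 1 − 2/π = 0.363 of its variance. Then r·u/√(1 − r² + r²u²) gives 0.19 / 0.33 / 0.51, and fixed-adjustment power falls to 81 / 84 / 90%. This is the worst case.

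**Step 5: strata left out.** If balanced strata explain a share R² of the variance, the arm difference has 1 − R² of the variance that the unadjusted test assumes. The test then rejects a true null when |Z| > 1.96/√(1 − R²) = 2.07 / 2.19 / 2.34 for R² of 10 / 20 / 30%, which is 3.9 / 2.8 / 1.9% of the time. Simulation with two binary strata and blocks of four (both assumed) gave 4.1 / 3.1 / 2.2%. Power was 81 / 82 / 84%, against 84 / 88 / 92% with the strata in the model.

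**The case against.** The SAP never says 'within-subject'. In covariate selection the phrase often means variance left unexplained overall, and on that reading power is within a point of fixed adjustment. The tested term is not named either, and if it is drug-by-beverage nothing is lost. So the loss needs two ambiguities to fall the same way.

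Correlations of 0.5 to 0.7 are most plausible for baseline craving. If that baseline is entered separately for alcohol and water, it varies within subject and the rule can keep it; how often depends on its cue-specific signal (59% of 600 runs in one weak set-up). At r = 0.3 the gain is about 3 points with complete data, and 1 point with 5% missing, which is within simulation error. Scattered missing ratings are themselves an assumption, as all six come from one computer-recorded session of about two hours. The amendment log does not describe the stratified randomisation in detail.

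All of this stands as a limit on size. It does not remove the point. The total-variance reading avoids the loss largely because almost any covariate passes it, so the rule then hardly selects. Two competent analysts following the same sentence could fit different primary models. And on any reading, sex and hs-CRP must first pass a significance screen on trial data before they can enter.

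**Conclusion.** The concern holds. The mechanism is exact for subject-constant main effects in complete data with a non-boundary fit: on the within-subject reading the rule discards every such covariate, however prognostic. On the assumed inputs, the cost at the alcohol cue is about 3, 10 and 18 power points at correlations of 0.3, 0.5 and 0.7, or about 1, 4 and 10 after worst-case range restriction. Omitting strata that explain 10 to 30% of the variance lowers type I error to about 4 to 2% and costs 3 to 8 power points (84 − 81 to 92 − 84).

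Confidence is high for the mechanism and moderate for the size, since effect, ICC, correlations and stratum strength are all assumed. The result is lost precision and an undetermined primary model, not bias or false positives. It should be fixed, and the fix is cheap.

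**What to change.** In the primary model, replace screen-and-retain with covariates fixed in advance:

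- the Visit 1 mini-cue VAS craving rating, either beverage-specific or as a baseline with its beverage interaction;
- sex and hs-CRP, in the form used for stratification.

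Keep the other candidates for sensitivity analyses. If a retention rule stays for secondary outcomes, state which variance component it refers to, the estimator, and the reduction required.

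The cost is a few sentences of SAP text and about 3 to 4 degrees of freedom. No new data are needed: the VAS is already rated at screening, and the strata are known at randomisation.
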